Subjects will complete the Lake Louise Questionnaire (LLQ) and Environmental Symptoms Questionnaire (ESQ) to determine acute mountain sickness (AMS). Subjects will be instrumented with a pulse oximeter to measure oxygen saturation (~15 minutes).

Lastly, subjects will have resting ventilation and HCVR measured (~15 minutes).

Day 4 – VO₂max testing day: Cardiopulmonary Lab, Eugene, OR (~30 min)

Subjects will perform a VO₂max test (~30 minutes). Additionally, resting, exercise, and post-exercise heart rate and systemic blood pressure will be measured. Any subject with child bearing potential will be required to take a pregnancy test prior to the VO₂max test.

All subjects will arrive at the Cardiopulmonary lab and will be given a telemetric core temperature pill to take 5-10 hours before arriving for **Day 5** testing. If subjects do not take the pill the night prior to exercise testing, they will have to take the temperature pill as a suppository the morning of testing.

To take the core temperature pills, subjects will be told to swallow with a glass of water or other beverage. There are no restrictions for fluid or food consumption after the pill has been ingested and subjects will be told not to chew the telemetric pill. In order to insert the pill as a suppository, subjects will be instructed to insert the pill past the first digit of your finger and given lubricant and a glove to assist with the insertion process. Research staff will be available to give additional information about the insertion process if subjects have more questions. These directions apply to every time subjects take the core temperature pills.

Day 5 – Performance Stabilization, Eugene, OR (occurs ~30 days before departure for Colorado) (~30 min)

To further ensure accurate baseline measurements of physical performance, the top 80 subjects (and 20 alternates) with the most similar physical characteristics will repeat the 5K. This strategy will minimize the influence of learning effects associated with the tests and facilitate matching between groups. (~30 min).

Day 6 – Hemoglobin mass, Eugene, OR (occurs ~30 days before departure for Colorado) (~75 min)

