5. Code Substitution—Simultaneous, a measure of visual scanning and attention, learning, and immediate recall of digit-symbol pairings;
6. Code Substitution—Delayed Recall, a measure of short-term memory for digit-symbol pairings;
7. Spatial Discrimination, a measure of visuospatial analytic ability;
8. Matching to Sample, an assessment of attention and memory for visuospatial discrimination;
9. Sternberg's Memory Search, a measure of working memory for letters.

The total time required to complete the battery of tests is ~20 minutes. DANA will be administered once at sea level (baseline day 3) and in the evening of days 1, 3, 7, and 13 at high altitude.

Acute Mountain Sickness (AMS) and oxygen saturation (SpO₂): The severity of AMS symptoms will be determined using a subset of the Environmental Symptoms Questionnaire (ESQ) and the Lake Louise AMS Questionnaire (LLQ), the two most common and accepted measures of AMS.

The ESQ is a self-reported, 68-question inventory used to document symptoms induced by high altitude and other stressful environments. A weighted average of scores from 9 symptoms (headache, lightheaded, dizzy, etc.) designated AMS-C will be calculated. AMS-C scores greater than 0.7 are considered positive for AMS (77).

The LLQ consists of a six question self-reported assessment of AMS symptoms, with a score of ≥ 3 , including headache, defined as AMS. The high altitude-illness assessment questionnaires will be administered on paper forms and tabulated in digital format at the end of each day (78).

After completing the AMS assessment forms, arterial saturation will be monitored by pulse oximetry. Each AMS assessment and pulse oximetry measurement will take ~10 minutes to complete. These measurements will be made once at baseline, immediately upon arrival at high altitude, and every night and morning of days 1, 2, 3, 7, and 13 at high altitude. Based on our previous study of 164 subjects, this ascent profile induced symptoms of AMS in ~50% of the subjects on the first evening at high altitude.

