The researcher will first verbally explain the study in its entirety and in doing so walk through the informed consent in person or via an online video conferencing service. Subjects will then be given a sufficient length of time to read through the informed consent form privately and instructed/encouraged to write down or remember any questions/concerns they may have. Afterward, the researcher will rejoin the subject and address any question or concern they may have while subsequently going back through the informed consent form with the subject and obtaining any needed initials and signature at the end of the document. Furthermore, the investigator will verbally address any questions the subject may have regarding the seriousness and/or likelihood for the occurrence of the risks described in the Informed Consent Form. The research team will address probability and severity of any adverse reactions with the subject by carefully explaining the statements regarding probability and severity contained within the Informed Consent. The investigator will also provide appropriate statistics (where available) regarding the probability of adverse reactions. The investigator also advises the subject of what he/she can expect to feel during a particular procedure, for example, during contrast injection. Investigator further explains any questions regarding physiology or reason for a particular procedure in plain language.

This process will be done either in person when they arrive for their physical exam and informed consent visit or done via an online video conferencing service prior to coming to the lab for their physical exam. Remote informed consent via an online video conferencing service will be conducted in groups sized 1-20, and we will allow individual subjects to ask questions privately in breakout rooms. Subjects will be asked to sign the informed consent once they arrive for their first visit to the lab.

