The most common symptoms of high altitude exposure are feeling lightheaded, dizzy, or short of breath during exercise. We expect up to 40% of people to feel one of these things while at high altitude. A smaller number of people will develop acute mountain sickness (AMS). AMS is a name for the combination of headache and lack of appetite, difficulty sleeping, upset stomach, throwing up, or feeling weak. These symptoms are usually temporary and manageable. They typically do not threaten peoples' health. Participants will not be treated for AMS symptoms and AMS should be gone by day 3 at the altitudes studied and therefore very unlikely to overlap with COVID symptoms and COVID testing will occur 4-5 days after arrival to Colorado to confirm the presence or absence of COVID infection. In addition, while PFO+ subjects have shown to have increased susceptibility to AMS, this illness is non-life threatening and does not increase risks for those with a PFO traveling to altitude. More severe altitude illness will be identified and treated as outlined below.

Traveling from sea level to high altitude can, in rare occasions, lead to more serious conditions. Two of these include high altitude pulmonary edema (HAPE) and high altitude cerebral edema (HACE). Both of these conditions are potentially fatal if left untreated. HAPE is a serious disorder that sometimes occurs with a fast change in altitude (going up). It occurs in less than 1% of people going from baseline to altitudes used in this study. The APFT will be at 9,075 feet above baseline. The uphill hike will start at 10,627 feet and go to 12,595 feet. Subjects will sleep at 10,570 feet. This sleeping altitude is not expected to produce HAPE. HAPE symptoms are treatable if found early. They usually show up 2-3 days after ascent to high altitude. HAPE may be preceded by AMS. The inability to breathe while resting is the hallmark of HAPE. Subjects may also have a bad cough, blue lips, fever, or fast heart beat. Subjects will be instructed to immediately notify study personnel if they feel out of breath at rest. Suspected HAPE cases will be treated by a doctor familiar with the condition.

The other serious complication of high altitude is HACE. HACE is very rare. The possibility of seeing HACE is extremely low. In our previous studies involving >150 volunteers at these altitudes in Colorado, HAPE and HACE have never been seen. As with HAPE, it is treatable if recognized early.

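### The risk section ranks AMS below an up-to-40% symptom rate, while the methods report symptoms of AMS in about 50% on the first evening alone

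*Combined protocol and SAP*

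**What the plan says.** Two places in the Research Plan give a frequency for altitude symptoms.

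- **Section G, Altitude associated risks.** The commonest symptoms are listed as lightheadedness, dizziness, or breathlessness on exercise, with "We expect up to 40% of people to feel one of these things while at high altitude". The next sentence is "A smaller number of people will develop acute mountain sickness (AMS"), and AMS is described there as headache combined with other complaints such as poor appetite, poor sleep or vomiting. No number is given for AMS.
- **Section C, Acute Mountain Sickness and oxygen saturation.** "Based on our previous study of 164 subjects", the plan says, "this ascent profile induced symptoms of AMS in ~50% of the subjects on the first evening at high altitude". The same subsection defines AMS in two ways: a Lake Louise score of at least 3, "including headache, defined as AMS", and, on the Environmental Symptoms Questionnaire, "AMS-C scores greater than 0.7 are considered positive for AMS (77").

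Section E (Informed Consent Process) says that the probability statements in the consent form will be explained to subjects, and adds: "The investigator will also provide appropriate statistics (where available) regarding the probability of adverse reactions".

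**The concern.** Section G ranks AMS below a group of symptoms that is itself capped at 40% for the stay. Section C reports about 50% for a single evening on what it calls this ascent profile. The proportion affected at any time during a stay cannot be smaller than the proportion affected on its first evening, so a whole-stay figure below 40% does not fit.

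About 50% is the highest rate that the plan gives for any harm. Section G also says that AMS symptoms will not be treated, so their expected frequency matters to anyone judging the burden of taking part. Section G already cites the team's earlier volunteers when it discusses HAPE and HACE, but it does not use the team's own AMS figure.

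**Working it through.** The plan gives no count behind the 50%, and no sample-size or power calculation for AMS to reproduce. The check compares the two stated rates.

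**Inputs**
- Section G: up to 40% with the commonest symptoms during the stay, and AMS in fewer people than that.
- Section C: about 50% with symptoms of AMS on the first evening, n = 164.
- Section C, Day 5 (Performance Stabilization): "the top 80 subjects (and 20 alternates) with the most similar physical characteristics will repeat the 5K". I take 80 as the number going to altitude and show 100 as well.

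**Step 1. Expected numbers**

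| Subjects | Section C, first evening (50%) | Section G, whole stay (below 40%) |
|---|---|---|
| 80 | 0.50 × 80 = 40 | fewer than 0.40 × 80 = 32 |
| 100 | 0.50 × 100 = 50 | fewer than 0.40 × 100 = 40 |

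**Step 2. Could rounding or chance in the earlier study explain the gap?** Taking about 50% as 0.50 × 164 = 82 subjects, the Wilson 95% interval has
- centre (p + z²/2n) / (1 + z²/n) = (0.5 + 0.0117) / 1.0234 = 0.500
- half-width z√(p(1−p)/n + z²/4n²) / (1 + z²/n) = 1.96 × 0.0395 / 1.0234 = 0.0756

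The interval is 42.4% to 57.6%, which excludes 40%. If the true rate were 40%, the exact binomial probability of 82 or more out of 164 is 0.006. Because the plan says only about 50%, I varied the count:

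| Assumed count | Rate | 95% interval |
|---|---|---|
| 74/164 | 45% | 37.7% to 52.8% |
| 78/164 | 47.5% | 40.1% to 55.2% |
| 82/164 | 50% | 42.4% to 57.6% |

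At 45% the interval reaches below 40%, but the estimate stays above it.

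**Step 3. The two readings of the 50% figure**
- *AMS by a questionnaire cut-off.* The statements contradict each other directly: about 50% on one evening against fewer than 40% over the stay.
- *Any AMS symptom.* Fewer than 40% could then have the syndrome, so the sentence on AMS could be true. The statement about the commonest symptoms still does not fit. Section C's examples of AMS-C symptoms include lightheadedness and dizziness, two of the three symptoms that section G calls the commonest and caps at 40%. A group of AMS symptoms seen in about half the subjects on one evening is more common than that.

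**The case against.** The strongest reply is that symptoms of AMS are not the same as AMS. Section C separates symptoms from a diagnosis, and section G speaks of people who develop a combination of complaints. The 40% also covers a partly different symptom list. This stands as far as it goes: it narrows the gap and shows that section C needs a definition. It does not close the gap, for the reason given in the second reading above.

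A second reply is that iron or EPO may lower the rate. If placebo stayed at 50% and allocation were equal (the plan states no ratio), the two active arms would have to average (3 × 0.40 − 0.50) / 2 = 35% for the trial as a whole to reach 40%. That is a 30% relative reduction, and section G makes no such argument. It says instead that PFO-positive subjects are more susceptible to AMS. The treatments and PFO mix of the earlier study are not described, so the rate could move either way.

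Three stronger readings are tempting, and the documents do not support them.
- A reader might infer that participants are told the lower figure. The consent form is not among the documents, and section E's commitment to give available statistics could include the 50%.
- A reader might infer that the 50% is the control-arm rate for Aim 3, so that the discrepancy changes the trial's power. The plan states no control rate, effect size, allocation or power for that aim.
- A reader might take 50% as the AMS rate to be quoted everywhere. Section C reports symptoms on one evening and names no cut-off.

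**Conclusion.** The point holds as an internal inconsistency in risk disclosure; nothing in the plan is miscalculated. Section G places AMS below 40% for the stay, while the team's own figure is about 50% with symptoms of AMS on the first evening. For 80 subjects that is about 40 on one evening against fewer than 32 over the stay. The Research Plan is written for IRB review, so the understatement reaches the IRB whatever the consent form says.

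This rests on three assumptions: that about 50% is close to 82 of 164, that the earlier ascent is comparable (section C calls it this ascent profile), and that about 80 subjects travel. If the 50% means any symptom, the conflict is weaker and lies in the ranking and cap of the commonest symptoms. No endpoint or analysis changes. The correction should still be made, because it costs little and replaces a vague ranking with a figure that the team already holds.

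**What to change.** Reconcile section C (AMS and oxygen saturation) with section G (Altitude associated risks):

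1. In section G, replace the unquantified ranking of AMS with the observed result: about 50% with symptoms of AMS on the first evening, n = 164, from the team's earlier study on this ascent profile.
2. In both sections, state what the figure counts (any AMS symptom, Lake Louise positive, or AMS-C positive) and its time window. If it counts any symptom, add the rate by cut-off from the same study if it is available.
3. Correct the up-to-40% statement so that it is consistent with that figure, and give its own source and window.
4. Check the consent form against the same figure, definition and window.

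The cost is a wording amendment and a less favourable stated risk. No procedure, schedule or analysis is altered.

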Overview: The initial components of the study will be performed over 6 days at baseline to 1) screen subjects for inclusion in the study and 2) obtain baseline measurements, with all studies conducted at the Cardiopulmonary Lab, Eugene, OR. These screening and baseline studies will be followed by 4 weeks of placebo or drug interventions (Cardiopulmonary Lab, Eugene, OR) and 14 days living at high altitude (Breckenridge or Leadville, CO). Within 1 week after returning to Eugene, OR, post-altitude measures will be made. Refer to Figure 1 below for a schematic representation of the timing and location of measurements. Each subject, regardless of intervention arm, will perform all protocols described below. All screening in Eugene, OR is scheduled for 6 days, but screening could take up to 10 days in the case of equipment malfunction or if the subject prefers to spread tests out over additional days.

* Indicates protocol that will be done on either day listed in early or mid altitude measures

What follows is a detailed description of each study day:

BASELINE: EUGENE, OR RESEARCH SITE

All studies done in Eugene will be done in either laboratory space within Pacific Hall and/or on running tracks and trails within the Eugene/Springfield metropolitan area or very close to this community.

Any subject with childbearing potential will be required to take a pregnancy test on VO₂max days and Hemoglobin mass testing days (both at baseline and altitude) as the other testing days will not involve any activity that would otherwise affect the fetus.

Day 1 – Informed consent, medical History, blood draw: Cardiopulmonary Lab, Eugene, OR (~60 min)

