Subjects who express interest in the study will have any initial questions answered on the phone or over email, depending on subject preference. Those interested in continuing with the study will arrive to the lab, and subjects will undergo informed consent and complete a self-report health history questionnaire, and complete a menstrual cycle history questionnaire (biological women only) (~30 min). Subjects will have the option to undergo informed consent remotely prior to arriving to the lab (see 'Informed Consent Process' below) but will complete all other paperwork, including signing the informed consent, upon arrival to the lab. Menstrual cycle history will be documented for control purposes for blood biomarker analysis, although subjects will not be required to be in a certain phase for testing, nor will they be excluded for contraceptive use.

After completing paperwork, subjects will undergo physical examinations by either a Nurse Practitioner or Physician Assistant 25 mL blood draw for iron, ferritin, transferrin, basic metabolic panel, and complete blood count measurements to be analyzed by QUEST. Subjects will be asked to either give or deny permission to the [name] Lab to re-contact them after the end of the study. Lastly, subjects will be asked to use an online Qualtrics survey, which will be emailed to every consenting subject, to log daily exercise activity for the duration of the study. (~30 min).

Day 2 – Army Physical Fitness Tests (APFTs): Cardiopulmonary Lab, Eugene, OR (~60 min)

Subjects will perform a modified version of the Army Physical Fitness Tests (APFTs) outdoors at the University of Oregon. The APFT will include 2 minutes of push-ups and sit-ups and a 5k run. Total time ~1 hour.

Day 3 – Lung function, cardiac screening, blood draw, Acute Mountain Sickness (AMS) questionnaire with finger saturation, and cognitive function testing: Cardiopulmonary Lab, Eugene, OR (~125 min)

Subjects will perform pulmonary function testing (~15 minutes) and cognitive function testing (~20 minutes).

Subjects will have an intravenous catheter (IV) placed. Subjects will then undergo comprehensive ultrasound screening. Amount of blood flow travelling through the PFO/ASD and IPAVA will be graded using saline contrast echocardiography while the subject is breathing room air. Pulmonary artery pressure, cardiac output, and TAPSE will also be measured using ultrasound (~60 minutes).

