5k run: The 5-kilometer run will be performed as part of the APFTs at baseline (see above) and on its own on days 1, 7 and 13 in Colorado. The run will be performed on a 400 m track or local running trail (Pre's trail) in Eugene, OR and on the high school track or local paved trails near the research site in Colorado. Subjects will be asked to complete the run as fast as possible while being timed.

Drug intervention: In a single-blind, randomized, placebo-controlled design, subjects will receive a placebo (saline placebo), iron, or erythropoietin.

Iron. Volunteers will receive an intravenous injection of Fe(III)-hydroxide sucrose (200 mg) or placebo twice before high altitude exposure, once 4 weeks and once within several days before traveling to high altitude. All subjects will report to the lab as if they are receiving iron, but only those randomly assigned to the iron arm will receive iron. The remaining subjects will receive intravenous saline. This is infused over the course of approximately 2-5 minutes. This is the same dose shown to prevent AMS, and to block hypoxia-induced pulmonary hypertension²⁸. All subjects, regardless of whether they receive iron or placebo, will remain in the lab for an additional 15 minutes after administration to ensure they do not have an allergic reaction (see risks below) and to ensure placebo subjects are blinded to the treatment.

EPO. Volunteers will receive a sub-cutaneous injection of epoetin alpha 150 IU/kg injections given weekly (50 IU/kg 3 x week) for three consecutive weeks prior to high altitude exposure. This dose and timing match the AMS prevention study protocol of Heo et al.¹¹

To ensure subjects are blinded to the intervention, all subjects will have the same intervention schedule. For those in the iron group, they will come to the lab 3x per week as required by the EPO intervention schedule, for example, and receive saline interventions. For those in the EPO group, they will come to the lab one time 4 weeks prior to departing to Colorado to receive a placebo injection while the iron group receives their iron injection. The placebo group will receive saline at all visits.

The table below provides the intervention schedule for each group. Blue indicates the placebo group, red indicates the iron group, and green indicates the EPO group.

	Sunday	Monday	Tuesday	Wednesday	Thursday	Friday	Saturday
4 weeks until departure				Saline Iron Saline			

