VO₂MAX testing: Subjects will perform a VO₂max test where they exercise to volitional exhaustion. Criteria for terminating a VO₂max include achieving: 1) heart rate >85% of age-predicted max (220-age), 2) a plateau in oxygen consumption and/or a respiratory exchange ratio >1.15; all of these criteria are continuously monitored on our metabolic system and Nellcor pulse oximeter. This carries the rare risk of dizziness, confusion, nausea, fatigue, difficulty breathing, abnormal heart rhythms, stroke, heart attack, and sudden death. In subjects less than 35 years old, the risk of sudden death of all causes is estimated to be 1 in 133,000 for men (Van Camp et al MSSE 1995). In this study only 100 of 136 deaths with identifiable causes were caused by cardiac events, so this estimate of risk may overestimate incidence of cardiac events. In the event of a cardiac event, research personnel will respond in a manner appropriate to their level of training. All graduate students, study coordinators, and PIs are minimum CPR/AED/first aid certified and will therefore immediately call emergency services and perform CPR if appropriate. The overall risk of sudden death caused by a heart problem for all ages and sexes is estimated to be 1 in 15,000 to 18,000. (Source: American College of Sports Medicine - ACSM). As such, the **probability** of the adverse reactions discussed above is low, and the **severity** is very low (e.g. dizziness) to very high (e.g. sudden death).

Additional exercise tests (APFTs, 5k run, and rucksack carry): Hard exercise has inherent risks associated with it, including stroke and heart attack. These risks are very low in young, healthy individuals (less than 0.00006%). Subjects may also feel dizzy, lightheaded, or unusually winded. These symptoms can be worse during exercise at high altitude. If subjects feel faint or feel like they

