minimize these risks, all precautions and warning labels will be followed, and dosing volumes will be strictly adhered to. Serious [allergic reactions](#) to this drug are unlikely, but may include: [rash](#), [itching/swelling](#) (especially of the face/[tongue](#)/throat), severe dizziness, [trouble breathing](#). Subjects will be excluded from the study for any health problems that may negatively effect their reaction to these drugs (see table of inclusion and exclusion criteria and drug appendices for specific exclusion criteria). FDA recall lists for drugs being administered to participants will be checked weekly beginning with the initiation of drug administration.

Risks for subjects who are pregnant: Potential risks to subjects who are pregnant (beyond the risks outlined above for the general population) include exercising beyond than what is recommended by their doctor (see 'VO_{2max} testing' and 'additional exercise testing' above) and potential unknown risks to the child bearer or fetus from carbon monoxide inhalation (see 'Hb mass measurement' above). None of the additional risks described above are greater in those who are pregnant. Due to the increased risk of exercise testing and Hb mass measurements, any subject with childbearing potential will be required to take a pregnancy test on a day that involves maximal exercise testing (VO_{2max}) and Hb mass testing while at baseline and in Colorado, and if such a test comes back positive, they will be immediately excluded from the study. Therefore, there is no added risk to the child bearer or the fetus from any of the above-mentioned protocols, as they will not undergo those procedures. As such, the probability of an adverse reaction is zero, and the severity of an adverse reaction is zero.

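### The pregnancy paragraph calls the risk zero, but the Day 2 fitness test with its 5k run comes before the first pregnancy test on Day 4

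*Combined protocol and SAP*

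**What the plan says.** In Section G, the paragraph Risks for subjects who are pregnant names two potential risks beyond those of the general population: exercise that exceeds medical advice, and inhaled carbon monoxide. For exercise it points to the paragraphs on VO2max testing and on additional exercise testing. The second of these opens "Additional exercise tests (APFTs, 5k run, and rucksack carry): Hard exercise has inherent risks associated with it".

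The safeguard is a testing rule: "any subject with childbearing potential will be required to take a pregnancy test on a day that involves maximal exercise testing". The rule specifies VO2max and adds the Hb mass days. A positive result means immediate exclusion. From this the paragraph concludes that there is "no added risk to the child bearer or the fetus from any of the above-mentioned protocols, as they will not undergo those procedures", and that "the probability of an adverse reaction is zero, and the severity of an adverse reaction is zero".

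Section C sets the order of visits. Under Day 2, "The APFT will include 2 minutes of push-ups and sit-ups and a 5k run". The 5k run entry in the description of procedures covers the baseline run within the APFT and says: "Subjects will be asked to complete the run as fast as possible while being timed". The first pregnancy test appears under Day 4: "Any subject with child bearing potential will be required to take a pregnancy test prior to the" VO2max test. Day 1 lists consent, health and menstrual histories, a physical examination and a blood draw. No pregnancy test is listed for Day 1 or Day 2.

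**The concern.** The zero is argued from the testing rule. It is not offered as a general judgement about fit young volunteers. The argument works only if a test comes before every procedure that the paragraph counts as a risk. If one of those procedures is scheduled before any test, a subject with an unrecognised pregnancy can follow the plan exactly and still perform it.

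What is at stake is participant safety and the accuracy of a risk statement written for ethics review. Nothing here bears on the endpoints, the randomisation or the analysis.

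**Working it through.** No calculation in the plan stands behind the zero, so there is no figure to reproduce. The check sets the schedule beside the risk paragraph.

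**Step 1: which procedures the paragraph covers.** VO2max testing and Hb mass measurement are named. The APFT, the 5k run and the rucksack carry enter through the cross-reference to additional exercise testing.

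**Step 2: where each falls relative to a stated pregnancy test (Section C).** The visits are taken in their numbered order.

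| Session | Listed procedure | Stated pregnancy test |
|---|---|---|
| Baseline Day 2 | APFT with 5k | None that day and none earlier |
| Baseline Day 4 | VO2max | Same day, before the procedure |
| Baseline Day 5 | Repeat 5k | None that day; Day 4 test earlier |
| Baseline Day 6 | Hb mass | Same day, before the procedure |
| Altitude days 1, 7, 13 | 5k and Hb mass | Same day; order relative to the 5k not stated |
| Altitude days 2, 8, 14 | Rucksack carry | None that day; test the day before |
| Post-altitude | 5k | None that day; earlier tests at altitude |

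Day 2 is the only listed session with no pregnancy test at any time before it. By visit label the gap is 4 − 2 = 2. That is not a count of calendar days, because Section C allows the six screening days to spread over as many as ten.

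**Step 3: whether anything else before Day 2 closes the gap.**
- Section D excludes anyone who is pregnant or planning to be. This depends on what the subject knows.
- Section D (Detailed recruitment methods) uses phone or email questions and self-identification. These also depend on what the subject knows.
- The Day 1 menstrual history is recorded as a control for the biomarker analysis, not as a pregnancy screen.
- The Day 1 blood panel covers iron indices, a metabolic panel and a blood count. No pregnancy assay is listed.
- The Day 1 physical examination may raise suspicion, but no pregnancy test is attached to it.

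Together these make an undetected pregnancy on Day 2 less likely. They do not rule it out, and Section G does not rest its zero on them.

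**Step 4: the inference.** The paragraph says that pregnant subjects will not undergo the listed procedures. For Day 2 the schedule does not secure that, so a probability of zero does not follow. A severity of zero does not follow either: testing changes who is exposed, not how serious an event would be if it occurred.

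**The case against.** The best defence is that the plan already does a good deal. Pregnancy is an exclusion, there is screening before the first visit, and a clinician examines each subject on Day 1. Carbon monoxide is the one exposure for which Section G expressly names the fetus. It has a required test on every scheduled Hb mass day, explicitly beforehand at baseline. The exercise risk is worded conditionally, the volunteers are recreational athletes selected for fitness, and the Day 2 session is at low altitude. All of this stands, and it is why the point is low priority. It supports a statement that the risk is low. It does not support a statement that the risk is zero by reason of testing.

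Three stronger readings are tempting, and the documents do not bear them out.

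- A reader might infer that subjects run the altitude 5k on the strength of a much older test, because on days 1, 7 and 13 the test is required only on the day, and on day 1 the Hb mass measurement is in the evening after the run. No text places the test after the run. The stated purpose, to keep a subject who tests positive out of the procedures, points to testing first, and both baseline tests are explicitly beforehand. The order is unstated, so this is a clarification and not a gap of any given length.
- A reader might infer that Section C contradicts Section G, because Section C justifies not testing on other days "as the other testing days will not involve any activity that would otherwise affect the fetus". That sentence concerns the fetus. Section G presents exercise as a potential risk to the pregnant subject and names the fetus expressly only for carbon monoxide. The two can be read as addressing different things.
- A reader might infer that a 5k run harms a fetus. The documents do not say so, and that is not claimed here.

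**Conclusion.** The point holds, in narrow form. The zero-risk statement in Section G does not follow from the schedule, because the Day 2 APFT with its timed 5k precedes the first required pregnancy test on Day 4, and the earlier safeguards do not guarantee detection of an unrecognised pregnancy.

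The gap is one sea-level session per subject of childbearing potential. Section C has the APFT done once at baseline by all subjects, and Section D allows up to 300 volunteers to be screened. Neither the number of childbearing potential nor a pregnancy rate is given, so no expected number of exposed pregnancies can be derived.

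The conclusion assumes that the visits run in their numbered order and that no pregnancy test is done beyond those listed. Confidence is high for the Day 2 sequence and the wording. The altitude order is a clarification only. Low priority.

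**What to change.** 1. Require a pregnancy test for each subject of childbearing potential at the Day 1 visit or on arrival on Day 2, before the APFT, and add it to the list of test days. Arrival on Day 2 is the tighter choice if screening visits are spread out.
2. In Section G, replace the zero probability and zero severity with a statement that the risk is low given the exclusion, the pre-screening and the scheduled tests.
3. As a minor clarification, state that the tests on altitude days 1, 7 and 13 are done before the 5k.

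The cost is one more routine test per subject of childbearing potential, with no extra visit: Day 1 already includes an examination and a blood draw. The number of added tests cannot exceed the 300 volunteers who may be screened. If the roughly even sex split sought at enrolment also held at screening, which is an assumption, it would be at most about 300 × 0.5 = 150. Items 2 and 3 are wording changes.
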